3.2.6.15. ANALYSIS OF ADVERSE EVENTS

This section summarizes statistical analysis plans for adverse event endpoints. The following section provides details regarding safety assessments including definitions and procedures.

The safety analysis set will be the ITT analysis set which includes all enrolled patients for which treatment was initiated as defined as a recording of an incision time. To enhance comparability when comparing safety profiles, only controls selected into a PS subclass will be included in primary safety analyses. Assessment of the safety of the investigational

implant will include an evaluation of the incidence and severity of complications and adverse reactions associated with the treatment in the safety analysis set.

Adverse event rates will be summarized by type of AE and for specific AEs in two ways: 1) per patient incidence of specific AEs and classes of AEs and 2) by event, summarizing event counts by visit interval over time and accordance with FDA Guidance (CDRH 2004)³⁶.

Device and procedure-related events will be summarized by severity and relatedness. Event listings will be provided that include details such as relatedness, severity, onset and resolution status will be provided for all events and relevant subsets of events such as serious events and related events. The summary tables will indicate the type of adverse event, the total number of such events, and the number and the percentage of patients affected in each treatment group (“subject wise evaluation”) and also stratified by relation to device and severity. Data of drop-outs will not be presented separately, but possible bias will be discussed in the final report.

In addition to summary tables, the following AE listings will be constructed:

- AE Listing 1 All AEs Sorted by Device and Event Type
- AE Listing 2 All AEs Sorted by Device and Patient
- AE Listing 3 Unanticipated Adverse Device Effects
- AE Listing 4 Serious AEs
- AE Listing 5 Severe AEs
- AE Listing 6 Device Related AEs
- AE Listing 7 Serious Related AEs
- AE Listing 8 Severe Related AEs
- AE Listing 9 Procedure Related AEs
- AE Listing 10 Other AEs
- AE Listing 11 AEs among patients discontinued early
- AE Listing 12 AEs among patients who died

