3.2.6.3. STUDY DESIGN

The 188 control subjects from [REDACTED]
[REDACTED] will be used to form a valid control group for determining the safety and effectiveness of the Simplify Disc device. Effectiveness comparisons will be performed using sub

classification through propensity score (PS) quintiles (Rosenbaum and Rubin, 1983)¹⁷. This approach directly addresses potential selection bias inherent in non-randomized comparisons.

The PS model will be evaluated according to rigorous criteria (Imbens and Rubin 2015)¹⁸ using a published heuristic (Maislin and Rubin 2010)¹⁹. Applications of this heuristic have been recently published (e.g., Keenan, Maislin, et al 2014²⁰; Arnardottir, Lim, Keenan, Maislin et al 2014²¹; and Pak, Keenan, Jackson, Grandner, Maislin et al 2014²²). The heuristic is designed to identify 5 sub classes in which the groups to be compared share the same multivariate distribution of a comprehensive set of baseline variables. Within each sub class, subjects are therefore equally likely to have received the Simplify Disc or conventional ACDF. The propensity score is the observational study analogue of complete randomization in randomized experiments in the sense that its use is not intended to increase precision but only to eliminate systematic biases in treatment-control comparisons (Rubin 2008)²³. Moreover, the "propensity score technique allows the straightforward assessment [of] whether the treatment groups overlap enough regarding baseline covariates to allow for a sensible treatment comparison" (Yue 2007)²⁴.

The PS sub classes will be formed when the prospective enrollment is completed in the investigational group. The standard implementation of the PS sub classification including iterative 'trimming' of subjects from the extremes of the PS distributions for both the

17 Rosenbaum PR and Rubin DB. The central role of the propensity score in observational studies for causal effects. *Biometrika* 1983a, 70:41-55.

18 Imbens and Rubin D. *Causal Inference in the Social and Biomedical Sciences* Cambridge University Press 2015 (in press)

19 Maislin G and Rubin DB. Design of Non-Randomized Medical Device Trials Based on Sub-Classification Using Propensity Score Quintiles, Topic Contributed Session on Medical Devices. *Proceedings of the Joint Statistical Meetings* 2010, pg 2182-2196.

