3.2.6.4. SAMPLE SIZE ANALYSIS

The current study is designed to demonstrate non-inferiority using a non-inferiority margin equal to -10.0% at a 1-sided type 1 error rate of $\alpha=0.05$. Subclassification using propensity score (PS) quintiles will be used to minimize selection bias arising from the non-randomized device group comparison. Mantel-Haenszel stratified analyses accounting for PS subclass will utilized when testing the primary non-inferiority hypothesis. A total of 182 two-level investigational subjects will be enrolled and compared to two level ACDF control subjects. The pool of two level ACDF control subjects includes a sample size of N=188. The sample size analyses below demonstrate that these sample sizes are sufficient to test the primary non-inferiority hypothesis after accounting for loss-to-following and PS ‘trimming’ of controls during the observational design phase.

According to Table 28 contained in the [REDACTED] SSED, the overall success was achieved in [REDACTED] controls. Therefore, the control group Month 24 CCS probability was assumed to be 70%. The total control sample size reported in the SSED is N=188. Since selection into a PS sub class will be conducted without access to outcome data, it is assumed that 85% of the selected controls will have a complete Month 24 CCS endpoint. It is also assumed that up to 20% of the controls will be trimmed as part of the PS modeling process. Therefore, for purpose on initial sample size analysis, the control sample size is assumed to be $N = 188 * .85 * .80 = 128$.

It is noted that the 2-level [REDACTED] group experienced an [REDACTED] success rate. For the purpose of sample size analysis, it is assumed that the 2-level Simplify disc

group will have at least a small true superiority margin of 3.5%. That is, it was assumed that the true probability of Month 24 CCS for the investigational group is 75.0%. As noted above, the primary effectiveness hypothesis is non-inferiority with a non-inferiority margin of -0.10 to be tested using at one-sided $\alpha=0.05$. With these assumptions, 154 investigational device patients are required for 80% statistical power as determined using industry standard software (nQuery Advisor 7.0 module PTE0U-1).

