3.2.6.5. ANALYSIS SETS

The study contains two treatment arms with patients receiving either two-level Simplify Disc or two-level ACDF. The following subject groups or analysis sets will be used to complete the analysis of data.

- Intent-to-treat (ITT) analysis set: The ITT analysis set will include all enrolled patients in which treatment was attempted as defined by the recording of incision time and excluding training cases. Patients will be included according to their intended treatment device. Since the investigational and control treatments are to be performed at different institutions, it is not possible for subjects to receive the alternative treatment. Therefore, the ITT analysis set will be used in safety analyses.

- Primary Effectiveness (PE) analysis set: The PE analysis set includes all subjects in the ITT analysis set that are selected into a propensity score subclass. Primary effectiveness analyses will be conducted using the PE analysis set. Selection into a PS subclass is the observational study equivalent to being randomized. Intraoperative failures will be included in primary non-inferiority testing as composite clinical endpoint failures. Patients with no follow-up subsequent to surgery will be treated as having a missing primary composite clinical endpoint and will be handled according to the approaches outlined below.
- Per protocol (PP) analysis set: The PP analysis set will include patients in the PE analysis set that have no major protocol deviations including clinically significant deviations from inclusion or exclusion criteria. Secondary efficacy analyses will be performed using the PP analysis set.
- Training cases analysis set: Training case safety and effectiveness data will be summarized separately.
- Original Protocol (OP) analysis set: All patients enrolled in the original protocol prior to approval of the subject protocol with the [REDACTED] historical control will be analyzed separately to determine if they would meet the current patient enrollment criteria. OP safety and effectiveness will be summarized separately and compared to the ITT analysis set. Please note, due to the small sample size, these comparisons will lack statistical strength and will be provided for informational purposes only.

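### The adverse-event comparison uses PS-selected controls but specifies no PS-subclass-stratified estimate, so it can stay confounded by subclass mix

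*Combined protocol and SAP*

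**What the plan says.** Section 3.2.6.15 takes the ITT set as the safety set and then narrows the control side: "To enhance comparability when comparing safety profiles", "only controls selected into a PS subclass will be included in primary safety analyses". AEs are to be summarised as per-patient incidence and as event counts by visit interval. The tables give "the number and the percentage of patients affected in each treatment group", "also stratified by relation to device and severity". PS subclass is not named in any AE rate, table or listing, and no between-group estimate, interval or test is described.

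The PS method is set out in section 3.2.6.3 for effectiveness: "Effectiveness comparisons will be performed using sub"-classification by PS quintiles. Balance is claimed at subclass level: "Within each sub class, subjects are therefore equally likely to have received the Simplify Disc or conventional ACDF". The same section checks achieved balance after adjustment for subclass. Section 3.2.6.4 carries this into the primary test: "Mantel-Haenszel stratified analyses accounting for PS subclass will utilized when testing the primary non-inferiority hypothesis"; section 3.2.6.6 repeats it.

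Two further provisions matter. Section 3.2.6.3 keeps every device patient in the safety analyses, even any left without a subclass, and limits reporting on trimmed controls to their baseline data. Section 3.2.6.5 states "Therefore, the ITT analysis set will be used in safety analyses", without mentioning the restriction on controls.

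**The concern.** Choosing controls who fall into some subclass gives overlap. It does not give the two groups the same distribution across subclasses. If device patients are concentrated in some quintiles and controls in others, and AE risk differs between quintiles, the crude percentages mix case-mix with device effect. The bias can run in either direction. The plan deals with this for effectiveness by pooling within-subclass differences. For safety it takes the selection step and stops.

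Section 3.1 makes it a purpose of the study to show that the disc is no less safe than ACDF, and the control is historical, from other institutions. Readers will treat differences between the two columns of the AE tables as evidence on that purpose.

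**Working it through.** **The plan's own figures.** Section 3.2.6.15 states no AE rate, sample size or power. The sample-size figures reproduce and are not affected by this point: 188 × 0.85 × 0.80 = 127.8, i.e. 128 controls. With 128 and 154 patients and rates 0.700 and 0.735, SE = √(0.70×0.30/128 + 0.735×0.265/154) = 0.0539, and power = Φ(0.135/0.0539 − 1.645) = 80.5%, against 80% stated.

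**Group sizes for the AE comparison.** All 182 device patients (sections 3.2.6.3 and 3.2.6.4). Controls: 188 × 0.80 = 150.4, taken as 150, using the plan's 20% trimming allowance.

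**What the composite already adjusts.** Section 3.2.6.1 counts as failures any serious AE classed as implant associated or implant/surgical procedure associated, all secondary index surgeries, and neurological decline. These enter the PS-stratified primary test. Section 3.2.7.7 has three further causality classes: surgical procedure-associated, not related, and undetermined. Serious AEs in those classes, all non-serious AEs, the any-AE rate, and each composite component shown singly have no PS-adjusted analysis.

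**Illustration 1: five equal subclasses, zero device effect.** Assumed inputs. Each subclass holds 332/5 = 66.4 patients, and the AE rate within a subclass is the same for both devices. For each group, crude rate = Σ(nₖ × rₖ)/Σnₖ.

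Worked case (moderate imbalance, AE rate falling from 30% to 10%):

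| Subclass | 1 | 2 | 3 | 4 | 5 | Total |
|---|---|---|---|---|---|---|
| Device n | 23.1 | 29.8 | 36.4 | 43.0 | 49.7 | 182 |
| Control n | 43.3 | 36.6 | 30.0 | 23.4 | 16.7 | 150 |
| AE rate | 30% | 25% | 20% | 15% | 10% | |

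Crude rates are 18.2% (device) and 22.2% (control), a difference of −4.0 points with no true effect. All settings:

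| Device share, subclass 1 to 5 | AE rate 20% to 10% | AE rate 30% to 10% |
|---|---|---|
| 0.45 to 0.65 (mild) | −1.0 | −2.0 |
| 0.35 to 0.75 (moderate) | −2.0 | −4.0 |
| 0.25 to 0.85 (strong) | −3.0 | −6.1 |

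The Mantel-Haenszel difference, with weights n₁ₖn₀ₖ/(n₁ₖ+n₀ₖ), is 0.0 throughout. That is by construction, because rates within a subclass are equal. The crude bias is zero if the device share is constant across subclasses or the AE rate is flat.

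**Illustration 2: continuous score, zero device effect.** Assumed inputs: control score N(0,1) with the lowest 20% removed; device score N(d,1); AE risk 20% at score 0, rising by an odds ratio of 1.5 or 2.0 per SD. Trimming moves the control mean to φ(−0.842)/0.80 = 0.280/0.80 = 0.35, so the remaining imbalance is d − 0.35. Pooling uses quintiles of the combined sample at 182:150.

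| d (SD) | Left after trimming | Crude difference, OR 1.5 to 2.0 | After pooling, largest absolute value |
|---|---|---|---|
| 0.50 | 0.15 | 1.4 to 2.7 points | 0.10 |
| 0.75 | 0.40 | 3.2 to 6.0 points | 0.20 |
| 1.00 | 0.65 | 5.2 to 9.5 points | 0.44 |

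**Scale.** At 20% risk the standard error of a crude AE difference is √(0.20×0.80×(1/182 + 1/150)) = 4.4 points. Biases of 1, 6 and 9.5 points are thus about 0.2, 1.4 and 2.2 standard errors.

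**The case against.** **The AE tables are not the whole safety case.** A reader might infer that the safety conclusion rests entirely on unadjusted comparisons. The documents do not support that: the events most tied to the implant count as failures in the PS-stratified composite. This stands, and it narrows the gap to the events listed above.

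**Confounding is possible, not shown.** A reader might infer that the comparison will remain confounded. The documents give no PS distributions, AE rates or association between the two, so neither size nor direction can be known. Section 3.2.6.3 expects similar populations, which makes separations of 0.75 to 1.0 SD pessimistic. The fixed low-tail cut in illustration 2 is also not the plan's trimming procedure, which retains device patients and trims controls to resemble them. At 0.5 SD the bias is well under one standard error. All of this stands. A bias that no table adjusts for nevertheless adds to sampling error without being visible.

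**Within-subclass likelihood.** Taken literally, the statement that patients in a subclass were equally likely to receive either device would mean a constant device share, and crude tables would then be unbiased. But 182 against 150 is not an even split overall (182/332 = 0.55), and the plan itself pools over subclass for effectiveness and checks balance adjusted for subclass. It does not rely on a constant share.

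**Silence is not exclusion.** Section 3.2.6.15 states no safety hypothesis or test, so no formal claim rests on a crude estimate; sections 3.2.6.11 and 3.2.6.12 are redacted. This is fair. Still, section 3.2.6.15 presents itself as the summary of the AE analysis plans and speaks of comparing safety profiles. Silence leaves the choice open until outcomes are known.

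**Crude tables are needed.** They are. Keeping every device patient in safety is deliberate, and a patient without a subclass cannot enter a stratified estimate. The remedy must therefore be a supplement.

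**The analysis sets.** A reader might infer a contradiction between sections 3.2.6.5 and 3.2.6.15. Read with section 3.2.6.3, the set is clear: all ITT device patients plus PS-selected controls. Only a cross-reference is missing.

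**Conclusion.** The concern holds in limited form. As written, the plan restricts the controls for the sake of comparability but describes only crude between-group AE figures, although its own balance property applies within subclass. The comparison with ACDF can therefore be confounded by subclass mix for any AE, serious AEs outside the composite, solely procedure-associated events, non-serious AEs, and composite components reported singly.

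The size is illustrative: about 1 to 6 points under moderate assumptions, 9.5 at the extreme corner, and 0.5 or less after pooling. These figures rest wholly on assumed PS imbalance, AE risk gradients and 20% control trimming. Confidence is high about the omission and not about the amount of bias. The primary endpoint and its sample size are unaffected. The change should be made because it answers a stated study purpose at almost no cost.

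**What to change.** In section 3.2.6.15, add PS-subclass-stratified (Mantel-Haenszel) risk differences with 95% confidence intervals for any AE, serious AEs, device-related AEs, procedure-related AEs and secondary surgery, using the subclasses formed for effectiveness. Present these as a supplement. Keep the crude tables and listings with all device patients, and state that any device patient without a subclass appears only there.

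In section 3.2.6.5, add one sentence cross-referring to section 3.2.6.15: the comparative safety set is all ITT device patients plus PS-selected controls.

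The cost is this wording and a few extra table columns. No new data are needed, and the subclass variable will already exist, formed without access to outcomes (section 3.2.6.3).

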Subjects who complete their 24 month visit prior to the last study subject's completion of the 24 month visit will continue to be followed annually until the last subject enrolled has completed the 24 month evaluation. However, for the purpose of primary safety and efficacy evaluations, the study completion/ termination assessment will be made at 24 months postoperatively, or at an earlier time point if the subject withdraws or is withdrawn from the study.

Follow-up evaluations annually after 24 months will include:

- AP and lateral X-rays (plain films);
- Flexion-extension X-rays (used to determine range of motion);
- Lateral bending films;
- Radiographic core lab evaluations;
- Postoperative subject survey (medication and satisfaction)
- Dysphagia Handicap Index;
- NDI assessment;
- SF-36 Health Survey;
- Neck and arm pain questionnaires (neck, arm, left arm and right arm);
- Foraminal compression test;
- Physician perception of results;

- Neurologic evaluation;
- Gait assessment;
- Study related medications;
- Work status;
- Adverse events as defined by Section 3.2.6.1 and Section 3.2.7 of this protocol and.
- [REDACTED]

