3.2.7. SAFETY ASSESSMENT

3.2.7.1. ADVERSE EVENTS

An adverse event is defined as any clinically adverse sign, symptom, syndrome, or illness that occurs or worsens during the operative and postoperative periods of the trial, regardless of causality, that is not otherwise being measured in the trial. This does not necessarily include immediate postoperative sequelae (such as chills, sore throat, nausea, vomiting, constipation, short-term fever unrelated to infection, straight catheterization, pain or burning during urination, etc.), unless it prolongs hospitalization or, in the opinion of the investigator, should be reported. Adverse events, whether or not device related, must be reported on the appropriate case report form. Any adverse event that occurred prior to treatment with the medical device will be documented in the patient's pre-operative medical history. Only adverse events which are new or have worsened during the course of this study will be evaluated in the safety assessment.

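### Section 3.2.6.15 compares per-patient AE incidence as a crude percentage, with no onset limit stated there and no allowance for time at risk, although time observed can differ between and within the groups

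*Combined protocol and SAP*

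**What the plan says.** Section 3.2.6.15 plans a comparison between groups: "To enhance comparability when comparing safety profiles, only controls selected into a PS subclass will be included in primary safety analyses". It gives two summaries. The first is "per patient incidence of specific AEs and classes of AEs", and the tables will show "the number and the percentage of patients affected in each treatment group". The second is by event, "summarizing event counts by visit interval over time". No Kaplan-Meier, person-time or number-at-risk summary is named, and no onset limit is given. On early leavers it says: "Data of drop-outs will not be presented separately, but possible bias will be discussed in the final report". The same section also plans AE Listing 11, which covers AEs in patients who stopped early.

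Section 3.2.7.1 counts as an AE anything that "occurs or worsens during the operative and postoperative periods of the trial". Under Section 3.2.5.4.2, patients who pass Month 24 before the last patient does "will continue to be followed annually until the last subject enrolled has completed the 24 month evaluation", and AEs are among the items collected at those annual visits. Sections 3.2.4.3 and 3.2.5.4.5 extend follow-up until FDA no longer requires it.

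Section 3.2.5.4.2 also says, and Section 3.2.5.4.5 repeats in substance, that "for the purpose of primary safety and efficacy evaluations, the study completion/ termination assessment will be made at 24 months postoperatively", or at earlier withdrawal. Section 3.2.4.2 takes the 188 controls from a separate completed randomized trial. Parts of that section are redacted, and the visible text does not say how long AEs were collected there.

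**The concern.** A crude percentage of patients affected rises with the time each patient is observed and falls when patients leave early. If device AEs with onset after Month 24 enter the numerator, while control AEs stop at another time, the difference between groups mixes a device effect with a difference in follow-up. The visit-interval table does not repair this, because it counts events rather than patients and has no stated number at risk.

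At stake is how the safety profile reads against fusion. Longer device observation would make the device look worse than it is. Longer control observation would do the opposite and could mask a harm. With a historical control the observation times are set by two separate studies, so nothing in the design makes them equal.

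**Working it through.** **The plan's own figures.** No numerical figure is stated for the AE analysis, so there is none to reproduce. The check compares the sections and then sizes the effect under stated assumptions.

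**Is a window stated?**
- Sections 3.2.2.2 and 3.2.6.1 limit the composite explicitly to data from the first 24 months.
- Sections 3.2.5.4.2 and 3.2.5.4.5 fix the time of the completion/termination assessment for primary safety at 24 months. They do not say which AE onsets count.
- Section 3.2.6.15 states no window and does not refer to those sections. Section 3.2.7.1 admits events from the whole postoperative period of the trial.

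**Inputs**
- From Section 3.2.6.4: up to 15% loss in the device group, and 85% of selected controls with a complete Month 24 endpoint. I read both as 15% loss, spread uniformly over 0 to 24 months.
- Assumed, because the visible text does not give them: uniform accrual over 12 or 24 months, data cut when the last patient reaches Month 24, constant hazard, true 24-month risk of 10% in both groups, and controls counted to 24 months only.

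**Step 1, hazard.** h = −ln(0.90)/24 = 0.00439 per month.

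**Step 2, device patients not lost, all AEs counted.** Follow-up is uniform from 24 to T months, with T = 36 or 48. Crude incidence = 1 − [exp(−24h) − exp(−Th)] / [h(T − 24)].
- T = 36: 1 − (0.9000 − 0.8538)/0.0527 = 12.3%.
- T = 48: 1 − (0.9000 − 0.8100)/0.1054 = 14.6%.

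**Step 3, patients lost before Month 24.** Average crude incidence = 1 − (1 − 0.90)/(24h) = 1 − 0.1000/0.1054 = 5.1%.

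**Step 4, combine with 15% loss in both groups**

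| Group | Calculation | Crude percentage |
|---|---|---|
| Control, capped at 24 months | 0.85 × 10.0 + 0.15 × 5.1 | 9.3% |
| Device, 12-month accrual, uncapped | 0.85 × 12.3 + 0.15 × 5.1 | 11.2% |
| Device, 24-month accrual, uncapped | 0.85 × 14.6 + 0.15 × 5.1 | 13.2% |

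The apparent excess is about 2 to 4 points with no device effect at all.

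**Step 5, same limit in both groups.** With onset capped at Month 24 in both, each group shows 9.3% and the gap from unequal follow-up is zero. What remains is understatement from loss: 10% reads as 9.3%, 20% as 18.6% and 30% as 27.9%. This affects the comparison only if loss differs between groups.

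**Step 6, if late events are captured only at completed annual visits.** With 12 months' accrual essentially no one has completed a Month 36 visit at the cut, so the gap is zero. With 24 months' accrual half have; incidence to 36 months is 1 − 0.8538 = 14.6%, the average is (10.0 + 14.6)/2 = 12.3%, and after loss it is again 11.2%.

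**Step 7, why a fixed day.** The Month 24 visit window is ±2 months. At the same hazard, incidence is 9.2% by 22 months and 10.8% by 26 months, so a limit at the visit itself still leaves some difference in time observed.

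**The case against.** The strongest reply is that the plan already points to 24 months for safety. Sections 3.2.5.4.2 and 3.2.5.4.5 tie the primary safety evaluation to that time, and Section 3.2.4.3 ties the marketing evidence to at least 24 months of follow-up. A reader might infer that the plan has no 24-month time point for safety at all; these sections do not support that. What stands against the reply is that they time an assessment without defining which AEs are counted, and that the authors wrote an explicit data window for the composite but not for the AE tables.

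A reader might also infer that study success is at risk. It is not. Serious implant-associated or implant/surgical-procedure-associated events and failure surgeries enter the composite, which is limited to 24 months in both groups. The AE tables carry no test, margin or decision rule.

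A third tempting reading is that AEs of early leavers are hidden. Listing 11 itemizes them, so the drop-out sentence conflicts with the section's own listings rather than removing the data. A listing still does not correct the percentage.

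Event counts by interval and onset dates in the listings do let a reader pick out late events. That stands, but it leaves the per-patient comparison as it is.

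Finally, the size depends on assumptions. Setting 12.3% to 14.6% against 9.3% would overstate it, because that applies loss to controls only while Section 3.2.6.4 plans on 15% in both groups.

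**Conclusion.** The point holds for the descriptive AE comparison. As written, Section 3.2.6.15 compares crude percentages with no stated onset limit and no time at risk, and the documents allow time observed to differ both between groups and among device patients.

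Under the constant-hazard illustration with a true 24-month risk of 10%, uncapped counting shows about 11.2% to 13.2% for the device against 9.3% for controls. This rests on assumed accrual of 12 to 24 months, equal 15% uniform loss and controls counted to 24 months. The gap is zero if Month 24 is applied to both groups, and also under annual-visit capture with 12 months' accrual. Because control follow-up is not visible, the actual direction is unknown, and it would reverse if control AEs were counted for longer. The change is worth making before outcomes are compared, but it does not affect the primary test.

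**What to change.** In Section 3.2.6.15:

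1. Limit the between-group AE comparison to events with onset up to one fixed Month 24 day limit, the same in both groups, and tie this to the 24-month statement in Sections 3.2.5.4.2 and 3.2.5.4.5.
2. Next to the crude counts, report the Kaplan-Meier (time-to-first-event) cumulative incidence at Month 24, censoring at withdrawal, at least for any AE, serious AEs, device-related AEs and procedure-related AEs.
3. Put events with later onset in a separate long-term table.
4. Reconcile the statement that drop-out data will not be presented separately with AE Listing 11.

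The cost is SAP wording and modest extra table programming. AE onset timing in the control data should be confirmed first; the visit-interval counts already planned need it in any case.
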